A prospective, single-arm, multi-center pivotal study designed to confirm the safety and effectiveness of The LimFlow System. The study will consist of a minimum of 60 and up to 105 subjects. This study utilizes a Bayesian Goldilocks adaptive design for sample size determination.

Number of Sites

Up to 25 sites in the United States, United Kingdom, and Japan

Primary Endpoint

Amputation Free Survival (AFS) defined as freedom from major amputation or death at 6 months, compared to a literature-based performance goal.

Major Amputation: above-ankle amputation of the index limb or

Death: all-cause mortality

Secondary Endpoints

Primary Patency: Defined as the absence of occlusion of the endovascular intervention maintained with no additional or secondary surgical or endovascular procedures, at 30 days and 6 months.

Primary Assisted Patency: Defined as the absence of occlusion of the endovascular intervention maintained with the use of additional or secondary surgical or endovascular procedures, as long as occlusion of the primary treated site has not occurred, at 30 days and 6 months.

Secondary Patency: Defined as the absence of occlusion of the endovascular intervention that is maintained with the use of additional or secondary surgical or endovascular procedures after occlusion occurs, at 30 days and 6 months.

Limb Salvage: Defined as the percentage of subjects with freedom from above-ankle amputation of the index limb, evaluated at 30 days, 3 and 6 months.

Change in Rutherford Classification: Defined as a change of one

STATISTICAL ANALYSIS PLAN

class or greater, as evaluated at 30 days, 3 and 6 months.

Technical Success: Defined as the successful creation of an arteriovenous fistula in the desired limb location with immediate morphological success.

Procedural Success: Defined as the combination of technical success, and absence of all-cause death, above-ankle amputation or clinically driven major re-intervention¹ of the stent-graft at 30 days.

Target Wound Healing: Defined as complete healing of the patient's target wound as evaluated at 30 days, 3, 6, 9 months, and 1 year.

All Wound Healing: Defined as complete healing of the patient's wounds as evaluated at 30 days, 3, 6, 9 months, and 1 year.

All Wound Area Reduction: Defined as reduction in area of the patient's wounds as evaluated at 30 days, 3, 6, 9 months, and 1 year.

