9.6 Exploratory Multivariate Analysis

Potential contributing factors for AFS failures will be investigated as follows:

Using frequentist Cox proportional hazards regression models, the following variables will be investigated in univariate models:

- Sex (Male/Female)
- Dialysis status (Yes/No)
- Age (≤ 70 , > 70)
- Diabetes (Type I, Type II, None)
- Race/Ethnicity
- Rutherford Classification
- Wound Area (continuous measure)

Any variable that is significantly related to AFS (at the 0.10 level) will be entered into a Cox multiple regression model. Variables no longer significant at the 0.05 level will be removed via backward elimination. The final model will be presented.

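### SAP 9.6 names as output only a Cox model chosen on its own p-values, so the surviving hazard ratios are biased away from 1; the unselected univariate results should stand beside it (minor)

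*SAP*

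**What the plan says.** SAP 9.6 is headed "Exploratory Multivariate Analysis". Its first step is described so: "Using frequentist Cox proportional hazards regression models, the following variables will be investigated in univariate models". The seven variables are sex, dialysis, age (70 or under, over 70), diabetes (three levels), race/ethnicity (levels not given), Rutherford classification and wound area as a continuous measure.

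The selection has two stages. First: "Any variable that is significantly related to AFS (at the 0.10 level) will be entered into a Cox multiple regression model". Then: "Variables no longer significant at the 0.05 level will be removed via backward elimination". The section closes: "The final model will be presented".

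It does not say which test is used (likelihood-ratio or Wald) or whether a multi-level factor is tested as a whole. It plans no shrinkage, no selection frequencies and no caveat on the p-values or intervals.

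Two neighbouring sections matter. SAP 9.2 (Protocol 11.6) gives posterior summaries of the AFS rate for each level of six of the seven variables, without selection. SAP 9.5 plans Cox heterogeneity analyses for five of them. Neither covers wound area.

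**The concern.** A variable reaches the final model only if its estimate happens to be large relative to its standard error. Reporting that estimate and its ordinary 95% interval as if the model had been fixed beforehand overstates the effect and the confidence in it. The stake is interpretive. The section exists to suggest contributing factors for AFS failure. A printed hazard ratio near 2.5 for, say, dialysis could be taken as a measured risk when the true value is 1.5, or when there is no effect at all. An exploratory label warns that findings are tentative. It does not tell the reader that the printed estimate is biased in a known direction.

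**Working it through.** **Inputs.** Thresholds 0.10 and 0.05 and seven variables (SAP 9.6). Sample size: "The study will consist of a minimum of 60 and up to 105 subjects" (SAP 1). Event-time hazards and 10% loss, uniform over 180 days (SAP 6.7). Degrees of freedom: 1 each for sex, dialysis, age, Rutherford and wound area, 2 for diabetes and at least 1 for race, so at least 8. Covariate prevalences, the number of race levels (2 to 4) and true effects are assumptions; the documents give none.

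**The plan's own figures.** SAP 9.6 states none. The nearest are the sample sizes in SAP 6.3, and they reproduce. With N=101, rejecting at 65 or more AFS successes gives one-sided alpha 0.0227 and power 0.909 at AFS 0.70 and 0.814 at 0.68. With N=56, rejecting at 38 or more gives alpha 0.0247 and power 0.915 at AFS 0.75. Dividing by 0.9 gives 113 and 63. The SAP 6.7 hazards return S(180)=0.54.

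**Events available.** N × (1 − AFS), before losses:
- N=105, AFS 0.70: 105 × 0.30 = 31.5 (30.5 on average in simulation after losses)
- N=82.5, the Table 2 average at AFS 0.70: 24.75
- N=60, AFS 0.75: 15

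**Chance findings.** Seven independent tests at 0.05 with no true effect: 1 − 0.95^7 = 0.302. Simulating the 9.6 procedure (2,000 trials per scenario, no true predictor), the share of trials with a non-empty final model was:
- 32 to 35% with likelihood-ratio tests (N=60 and N=105)
- 24 to 28% with whole-factor Wald tests
- 29 to 35% if factor levels are tested singly

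A second simulation gave 31%. The closed form alone accounts for most of this, so the rate comes mainly from multiplicity rather than from the two-stage selection.

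**Inflation, by hand.** For a binary variable with prevalence p and D events, SE(log HR) ≈ 1/√(D·p(1−p)). Take D=34.2 (the simulated average with one effect of HR 1.5) and assume p=0.5. Then SE=0.342, and significance at 0.05 requires an estimate above exp(1.96 × 0.342) = 1.95. So a true HR of 1.5 can be kept (in the right direction) only when it is estimated at about 1.95 or more. Under a normal approximation it is kept 22% of the time, with median 2.28 and coverage 88%. With p=0.3 these become 19%, 2.44 and 86%.

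**Inflation, by simulation** (N=105, AFS 0.70 in the reference group, likelihood-ratio tests):

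| True HR | Kept | Median HR when kept | Median HR, no selection | Coverage of nominal 95% CI when kept |
|---|---|---|---|---|
| 1.5 | 21% | 2.37 | 1.52 | 85% |
| 2.0 | 55% | 2.49 | 2.03 | 94% |

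The second simulation (N=105, about 30 to 35 events, prevalences assumed) gave 2.55 with 77% coverage at HR 1.5, against 1.45 and 95.5% unselected. A third, with four true effects at once and other assumed prevalences, gave 85 and 88% coverage at HR 1.5 and 91% at HR 2.0. The exact figures therefore depend on the scenario.

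For a variable with no effect that is nevertheless kept (N=105, AFS 0.70), the median HR away from 1 was about 2.5, and its interval included 1 in 0 to 26% of cases. A low figure is expected, since such a variable is kept because its p-value is below 0.05.

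**The case against.** The section is labelled exploratory, no success criterion uses it, and much of the harm that a reader might infer is not supported by the documents.

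- *Nothing but the final model will be reported.* The SAP names no other output but forbids none, and the univariate models are fitted in any case. The gap is that they are not committed to the report.
- *Dropped variables get no estimate.* SAP 9.2 supplies unselected AFS rates with credible intervals for six of the seven. What is missing is any hazard ratio, and anything for wound area.
- *The selection procedure creates false predictors in a third of trials.* The range is 24 to 35%, it turns on a test that the SAP does not name, and it is mainly multiplicity. Seven unselected 95% intervals carry about the same 30% chance that one excludes 1.
- *The procedure misses most moderate factors.* Low detection mostly reflects about 30 events. In a comparison with independent covariates, an HR of 1.5 for dialysis was kept in 15.5% of SAP final models and significant in 15 to 16% of full models.
- *A full seven-variable model should replace selection.* Nine parameters on about 30.5 events is 3.4 events each. Coefficients diverged in about 4 to 6% of runs in one simulation, and in about 10% in another that assumed 8% Type I diabetes.
- *Selection here feeds the SAP 9.5 adjustment.* SAP 9.5 does admit characteristics that predict AFS as candidates, but it does not say that they come from 9.6.

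These points stand and they limit the concern. None of them removes the bias in the hazard ratios that the section does undertake to present.

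**Conclusion.** The concern holds in a limited form. The surviving hazard ratios in SAP 9.6 are biased away from 1: about 2.4 to 2.5 for a true 1.5, and about 2.5 for a true 2.0. Their nominal intervals under-cover for null or moderate effects, at about 77 to 85% for HR 1.5; the deficit nearly disappears at HR 2.0 (about 94%), although some inflation remains. The direction follows from selecting and estimating on the same data. The sizes rest on assumed prevalences, N=105 and roughly 30 to 37 events; the inflation would be greater at the smaller sample sizes that the design allows. The matter is minor, because the analysis is exploratory and neither the primary test nor its conclusion is touched.

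**What to change.** Replace the last sentence of SAP 9.6 with:

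> Hazard ratios and 95% CIs from the univariate models will be presented for all seven variables, whether or not they are selected. The final model will be presented beside them, labelled as data-selected, with bootstrap selection frequencies and a statement that its p-values and intervals are not adjusted for selection and that no interval in this section is adjusted for multiplicity.

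A model containing all seven variables may be added as supportive, with penalised estimation if a coefficient does not converge.

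The cost is SAP wording, one table from models already planned, and a bootstrap run. The univariate intervals will be wide. The change takes selection bias out of the main table but does not reduce the number of chance findings, which is why the multiplicity statement is needed. Sample size, conduct and the primary analysis do not change.

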10 APPENDIX 1 – PERFORMANCE GOAL DERIVATION

A literature search was performed by the Yale Clinical Research Group (YCRG) according to a pre-specified protocol, and the search methods and results have been documented in a Literature Search Report (“Literature Search Report for the LimFlow System” Version 1.0 dated 19 December 2017). The literature search identified 36 publications meeting inclusion criteria that reported amputation-free survival (AFS), the composite of all-cause death or major (above-the-knee) amputation, all-cause mortality, major amputation, or wound healing in no-option CLTI subjects (patient with CLTI Rutherford score > 4 that are inoperable) who were receiving the standard of care (medication) or placebo.

Of the 36 publications, 27 publications reported the 6- or 12-month rate of amputation-free survival (or the composite of all-cause mortality or major amputation, which was converted into amputation-free survival) and contributed to the meta-analysis. Of these, 23 studies reported AFS at 6 months, and 19 reported AFS at 12 months.

In a review of the studies used for developing the performance goal, some noted that the studies that used Fontaine IV for the classification of critical limb ischemia had the highest AFS rates. Fontaine IV is a clinical assessment only, and though it is associated with Rutherford 5 and 6, it is less specific (see **Figure**).

STATISTICAL ANALYSIS PLAN

The specificity of the Rutherford classification assures that the population enrolled in the studies will have the level of disease expected in the LimFlow clinical trial. In studies that used Fontaine, the lack of specificity and objective criteria can lead to a broader population being included that might be considered Rutherford 4 not included in the current study.

Figure 2: Comparison of Rutherford and Fontaine

Fontaine Grade	Symptoms	Grade	Category	Clinical Description	Objective Criteria
Stage I	Asymptomatic, incomplete blood vessel obstruction	0	0	Asymptomatic – no hemodynamically significant occlusive disease	Normal treadmill* or reactive hyperthermia test
			1	Mild claudication	
Stage II	Mild claudication pain in limb	I	2	Moderate claudication	Resting AP<60mmHg, ankle or metatarsal PVR flat or barely pulsatile; TP < 40mmHg
			3	Severe claudication	
Stage III	Rest pain, mostly in the feet	II	4	Ischemic rest pain	Complete treadmill exercise; AP after exercise >50 mmHg ≥20mmHg lower than resting value
Stage IV	Necrosis and/or gangrene of the limb	III	5	Minor tissue loss – nonhealing ulcer; focal gangrene with diffuse pedal ischemia	Resting AP<60mmHg, ankle or metatarsal PVR flat or barely pulsatile; TP < 40mmHg
			6	Major tissue loss – extending transmetatarsally; functional foot no longer salvageable	

Studies that only used the Fontaine classification were compared to those that only used the Rutherford classification using logistic regression. The SAS code was:

```
proc logistic data=limlos_adj;
class study status class;
freq num;
model status(event='no event')= class;
run;
```

where status is whether there was a death or major amputation event at 6 months or not, the class was the CLTI classification system used (R or F), and num is the variable that contains the number of subjects with or without an event.

The results of the logistic regression are shown in **Table 6**. The classification system effect has a low p-value (p <0.0001) and an odds ratio (Rutherford 5 or 6 versus Fontaine IV) of 2.891.

Table 6: Results of Logistic regression predicting AFS using CLTI classification method

Analysis of Maximum Likelihood Estimates						
Parameter		DF	Estimate	Standard Error	Wald Chi-Square	Pr > ChiSq
Intercept		1	0.5020	0.0766	42.9900	<.0001
class	FIV	1	0.5308	0.0766	48.0546	<.0001
Odds Ratio Estimates						
Effect		Point Estimate	95% Wald Confidence Limits			
class FIV vs R56		2.891	2.141	3.903		

The 6-month AFS rates in studies shown in **Table 7** (reprint from Yale Clinical Research Group) that used the Fontaine classification were adjusted in two ways: a) the average of the percentage of Rutherford 5 or 6 in the other studies as reported in b) the odds ratio. The adjusted numbers were very similar between the two methods so for this document, the odds ratio adjusted numbers will be used. After the odds ratio adjustments,

STATISTICAL ANALYSIS PLAN

the final AFS rate point estimate was 42.0% with an upper 95% confidence limit of 51.2%. However, in acknowledgement of FDAs concern around the performance goal and the previous discussions since 2017, LimFlow is not proposing to change the previously communicated performance goal based on the prior Yale work where the AFS rate point estimate was 43.7%, with an upper 95% confidence limit of 53.5%. Since the hypothesis test for this study is a test for superiority, the performance goal is set at the upper 95% confidence limit (UCL) of 53.5%, rounded up to 54%.

**Table 7: Reprint of from YCRG:
Meta-analysis of 6-month AFS rate in no-option patients with Rutherford category 5 or 6 CLI**

Study	N	Event-free survivors (n)	Observed AFS Rate	Included Rutherford Categories	Observed Proportion R4	Observed Proportion R 5/6	Imputed Proportion R 5/6	Adjusted AFS Rate
Brass et al 2006 ³	177	146	82.5%	4, 5, 6	NR	NR	66.9%	59.3%
Teraa et al. 2015 ⁴	79	66	83.5%	3, 4, 5, 6	31.6%	63.3%	NA	58.3%
Dubsky et al. 2013 ⁵	22	10	45.5%	4, 5, 6	NR	NR	66.9%	32.7%
Iafrafi et al. 2016 ⁶	34	22	64.7%	5	0.0%	100.0%	NA	64.7%
Anghel et al. 2011 ¹¹	14	3	21.4%	4,5	50.0%	50.0%	NA	13.5%
Li et al. 2013 ¹²	29	23	79.3%	4, 5, 6	NR	NR	66.9%	57.0%
Benoit et al. 2011 ¹³	14	9	64.3%	4,5	50.0%	50.0%	NA	40.4%
Gupta et al. 2013 ¹⁴	10	8	80.0%	4, 5, 6	20.0%	80.0%	NA	64.7%
Szabo et al 2013 ¹⁷	10	4	40.0%	4, 5, 6	NR	NR	66.9%	28.8%
Belch et al. 2011 ¹⁸	259	196	75.7%	4, 5, 6	NR	NR	66.9%	54.4%
Losordo et al. 2012 ¹⁹	12	8	66.7%	4,5	41.7%	58.3%	NA	44.7%
Nikol et al. 2008 ²⁰	56	34	60.7%	4, 5, 6	NR	NR	66.9%	43.7%
Powell et al. 2012 ²¹	24	17	70.8%	4, 5, 6	NR	NR	66.9%	50.9%
Idei et al. 2011 ²²	30	3	10.0%	4, 5, 6	27.0%	73.0%	NA	7.6%
Pignon et al. 2017 ¹⁶	19	14	73.7%	4,5	35.0%	65.0%	NA	52.1%
Wang et al. 2018 ²⁴	36	28	77.8%	4,5	66.7%	33.3%	NA	43.5%
Faglia et al. 2010 ²⁵	27	3	11.1%	4,5,6	37.0%	63.0%	NA	7.7%
Dalla Paola et al. 2019 ²⁶	84	50	59.5%	4,5,6	NR	NR	66.9%	42.8%
Dubsky et al. 2019 ²⁷	44	31	70.5%	4,5,6	NR	NR	66.9%	50.7%
Faglia et al. 2012 ²⁸	12	3	25.0%	5,6	0.0%	100.0%	NA	25.0%
Simple Average			58.1%	Simple Average				42.1%
Weighted Average			68.3%	Weighted Average				49.2%
Meta-Analytic Average			58.6%	Meta-Analytic Average				42.0%
Min			10.0%	Min				7.6%
Max			83.5%	Max				64.7%
SD			24.1%	SD				17.7%

Meta-analytic estimate of the historical rate of AFS at 6 months in no-option R5/R6 CLTI patients is 42.0% (95% CI, 32.8-51.2).

STATISTICAL ANALYSIS PLAN

11 APPENDIX 2 — BAYESIAN MULTIPLE IMPUTATION METHODOLOGY

Multiple imputation inference involves three distinct phases⁵:

1. The missing data are filled in M times to generate M complete datasets.
2. The M complete datasets are analyzed by using standard procedures
3. The results of the M complete datasets are combined for inference.

This is accomplished in this study as follows:

1. The missing data are filled in M=10,000 times via the predictive model described in Section 6.5. The multiple imputation literature sometimes calls this the “imputer’s model,” but in our Bayesian framework, this is simply the posterior predictive distribution of unobserved data, after integrating out the parameters of the piecewise exponential model described in Section 6.5. This results in M=10,000 completed datasets.
2. The M complete datasets consist of binary outcomes (Event, No Event at 180 days) and are analyzed using the “analyst’s model,” which in this case is the conjugate beta / binomial model. Letting X_{obs} denote the set of observed binary outcomes and X^*_m denote the m^{th} set of imputed binary outcomes, the posterior probability distribution $f(\phi | X_{obs}, X^*_m)$ is a beta distribution. For each of the m completed datasets (X_{obs}, X^*_m), the posterior probability $\text{Prob}(\phi > 0.54 | X_{obs}, X^*_m)$ is easily computed from the c.d.f. of the corresponding beta posterior distribution.
3. Combining results from these 10,000 completed datasets is accomplished by integrating over the posterior predictive distribution of the imputed values. Numerically, it is as simple as computing the average of the M=10,000 posterior probabilities from Step 2. In particular, since

$$f(\phi | X_{obs}) = \int f(\phi | X^*_m, X_{obs}) \cdot f(X^*_m | X_{obs}) dX^*_m,$$

by Monte Carlo integration,

$$f(\phi | X_{obs}) = \int f(\phi | X^*_m, X_{obs}) \cdot f(X^*_m | X_{obs}) dX^*_m \approx 1/M \sum f(\phi | X^*_m, X_{obs}),$$

where the M realizations of X^*_m come from the posterior predictive distribution of $f(X^*_m | X_{obs})$. This is a linear combination of the M beta posterior densities. It follows that the c.d.f. $F(\phi | X_{obs}) \approx 1/M \sum F(\phi | X^*_m, X_{obs})$, and thus the posterior probability

$$P(\phi > 0.54 | X_{obs}) \approx 1/M \sum (1 - F(0.54 | X^*_m, X_{obs})),$$

which is the average of the M=10,000 posterior probabilities from Step 2.

A quantile q of the posterior distribution $f(\phi | X_{obs})$ can be computed by setting $q = 1/M \sum F(\phi | X^*_m, X_{obs})$ and numerically solving for ϕ using a root-finding algorithm. In this manner, a 95% Bayesian credible interval is computed from the 2.5th and 97.5th percentiles. A posterior median can be computed when q is set to 0.50. A posterior mean is computed as the average of the means of each of the 10,000 posterior beta distributions.

⁵ Molenbeerghs G & Kenward MG (2007), *Missing Data in Clinical Studies*, Wiley & Sons, page 106.
